Medical emergency: -Chest pains - Excessive bleeding - Fall and cannot get up - Difficulty breathing	If a research staff person encounters this situation while speaking on the phone, the person is put on hold and the staff person calls 911 immediately. If the situation occurs within the home, the staff person calls 911 immediately and stays with participant until help arrives. If the situation occurs in the rehabilitation setting, procedures for medical emergencies will be followed. [name] and [name] are informed immediately of the event, and they contact the individual for a follow-up within two days. Research staff member completes alert form and reports adverse event to IRB as required.
Threats to hurt self or others; severe depression; suicidality	Described later in text (Safety plans).
Evidence of abuse	Evidence of physical abuse is as follows: • Participant states to research staff that abuse occurs

	
 • Research staff observes physical evidence (black eye, black and blue marks on arms/legs) 
If the interviewer or OTs suspects child abuse, they will report this immediately to [name] or [name], who will discuss this with the Polytrauma Social Worker Case Manager. If there is reasonable cause to suspect child abuse, this will be reported to the Child Abuse Hotline with Child Protective Services [contact]). If the interviewer or OTs suspect spouse or partner abuse, they will report this immediately to [name] or [name], who will review the situation with the Polytrauma Social Worker Case Manager. Information and contact information for community resources (such as Philadelphia Domestic Violence Hotline and Women Against Abuse) will be shared with the family member who is being abused. If the interviewer or OTs suspect elder abuse, this will be reported to the appropriate agency.
 
The PI reports adverse event to the IRB as required. Note – The mandated reporting of child and elder abuse is stated in the consent form.

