Extreme Home Hazards (if observed during home visit).	
-Exposed electrical wires -External door missing or cannot be locked -Ceiling, floors caved in -No temperature control (no air or heat – must be extreme) -Major infestation
 
Research staff member notifies PI within 24 hours. If alert is identified prior to baseline/randomization, the individual is not enrolled in study until the home hazard is addressed. If enrolled in the study, the PI contacts participant and refers him/her to a home repair program.
 
PI completes Alert form.

Alerts and adverse events are reviewed at weekly meetings to assure that each has been managed appropriately and follow-up and resolution obtained. We expect adverse events to be infrequent. In the rare case in which multiple adverse events occur, the study team will meet to review the severity and cause and determine next study steps with the guidance of the IRB

Safety Plan

Given the population of interest (persons with TBI and depression), the team has developed a detailed safety plan for participants. The Rehabilitation Medicine Service and medical center employs mental health providers who can provide support to the study team for clinically emergent situations or circumstances that arise in the conduct of the research. A licensed clinician is always available at the medical center during business hours to facilitate assessment and support for emergent clinical situations. A licensed clinician is also available through the Behavioral Health Emergency Service during business hours and outside business hours.

If the interviewer or interventionists observe that a study participant is a threat to self or others or has severe depression, a safety plan is in place to manage this situation. If a research staff person encounters a situation in the rehabilitation clinic in which the person is severely depressed and threatens to hurt self or others immediately, or has answered affirmatively to item 9 on the

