PHQ, the research staff member stays with the individual and calls on the emergency behavioral health services at the medical center. Patient can be escorted to the BH urgent walk-in clinic on the 7th floor for immediate assessment. Patients can also be escorted to the emergency room where there is psychiatric staffing 24/7 for immediate assessment. If there is an established BH provider, a phone call will be made to try to make immediate contact. If the person is not an immediate threat to self or others, then the person is actively encouraged to contact his provider and/or the contact is made for the person if he/she chooses. The research staff also informs the person that a member of the research team will be contacting him/her shortly to follow-up. Immediately at the conclusion of the interview, [name] are notified of the situation. They contact the person to obtain further information and encourage immediate action. The team has compiled a list of community resources (VA and non-VA) that will be shared with subjects for appropriate mental health resources, crisis lines, financial resources, and other resources as needed.

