In the event that the interviewer or OT is meeting with the veteran in the home and assesses the veteran to be at high risk for suicide, or the veteran has answered affirmatively to the PHQ item 9 at baseline, or is very distressed, they will refer the veteran to the appropriate mental health resources and provide information on how to access these resources. During business hours, veterans can call the Mental Health Clinic staff at [contact] or come as a walk-in to the clinic for problems that need immediate attention. After business hours, veterans can phone the Corporal Michael J. Crescenz VA Medical Center psychiatrist on call for problems that need immediate attention; the veteran would call the main hospital number at [contact] and ask for the psychiatrist on call. If veterans are experiencing suicidal ideation, they can contact the Veterans Crisis Hotline at [name], call 911, or go to the nearest emergency room or the VA Medical Center's emergency room. When a veteran calls the [name] crisis hotline number, he reaches the national hotline, indicates if he/she is a veteran by pressing 1, and then the hotline contacts the VA Medical Center Suicide Prevention Team, which contacts the veteran's provider or arranges for a provider if the veteran does not have one. If veterans are experiencing homicidal thinking, they can call 911 or go to VA's emergency room or the nearest emergency room. The interviewer or OT will encourage the veteran to seek the appropriate services, but if the OT or interviewer judges that the veteran needs emergency services for a life-threatening medical or psychiatric emergency and is unable to contact these services, the OT or interviewer will call 911 for the veteran if in the home. The OTs and interviewer will also report psychiatric concerns to the [name], who will consult, as needed, with [name], a consultant, and [name], a co-investigator, Chief of the Medical Rehabilitation Service, who has expertise in VA resources available for veterans with TBI and mental health problems. As per VA IRB regulations, the PI will complete Adverse Event Reporting forms and report to the IRB, as required.

Training for the Safety Plan

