Training of our interviewer and interventionists in the safety plan will be reinforced on a regular basis. The OT co-investigator responsible for training the OTs in BA and overseeing their work, as well as [name], consultant on this project, have experience in delivering BA and safety plans for participants with depression and mental health crises. [name] has conducted several studies using BA to reduce depression and increase activity. Furthermore, [name] and [name] will provide education to the interviewer and OT interventionists on assessment of depression, signs of both suicide risk and warning signs of imminent suicide risk, how to respond and show support for participants at high risk for suicide, and how to connect veterans with suicide risk to appropriate resources/referrals. They will also provide training, along with [name], on the Columbia Suicide Severity Rating Scale.⁷⁸ The Columbia Scale will be administered to participants who answer affirmatively (1, 2, or 3) to item 9 on the PHQ-9,

indicating the presence and duration of suicidal ideation. The Columbia Scale is an assessment tool that evaluates suicidal ideation and behavior; it has been used with military and civilian populations. Outcomes on this scale that can be used for safety monitoring include scores on suicidal behavior lethality, suicidal ideation, and suicidal ideation intensity. It is evidence-based in that much research has validated its relevance and the effectiveness of its questions in assessing suicide risk. Triage guidelines are available for the tool that indicate risk and need for further evaluation and management (e.g., triggers for immediate referral to mental health services and patient safety precautions). Data from the PHQ item 9 and Columbia Scale will be shared when the person is referred for mental health services.

The consent form will state that the research team may refer the participant to appropriate medical and mental health resources within the VA medical center. The consent will also note that in the event that a participant indicates an intention to harm self or others, we will be obligated to notify the appropriate medical and mental health professionals immediately.

12. Privacy and Confidentiality

12.1. Describe whether the study will use or disclose subjects' Protected Health Information (PHI).

The study uses subjects' PHI but does not disclose it.

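### In the home-visit Safety Plan, the staff 911 call for a life-threatening psychiatric emergency depends on services being out of reach, and staff are not told to stay

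*Combined protocol and SAP*

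**What the plan says.** All of this is in Section 11 (Reporting) of the combined protocol and SAP.

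- **Alert table, medical emergency row.** "If the situation occurs within the home, the staff person calls 911 immediately and stays with participant until help arrives". The same row has staff call 911 at once if the emergency arises during a phone contact.
- **Alert table, psychiatric row.** The row "Threats to hurt self or others; severe depression; suicidality" contains no action and points to the Safety Plan.
- **Safety Plan, rehabilitation clinic.** The trigger reads: "the person is severely depressed and threatens to hurt self or others immediately, or has answered affirmatively to item 9 on the" depression questionnaire. The required response reads: "the research staff member stays with the individual and calls on the emergency behavioral health services at the medical center".
- **Safety Plan, home.** When a veteran is at high suicide risk, had a positive PHQ item 9 at baseline, or shows marked distress, the default for staff reads: "they will refer the veteran to the appropriate mental health resources and provide information on how to access these resources". Staff also encourage use of services and report psychiatric concerns to the study team. The staff 911 call rests on their own judgement of need, and its terms read: "for a life-threatening medical or psychiatric emergency and is unable to contact these services, the OT or interviewer will call 911".
- **Training for the Safety Plan.** Staff are taught the warning signs of imminent suicide risk and how to respond. Triage guidelines for the Columbia scale are described as including "triggers for immediate referral to mental health services and patient safety precautions". The consent form will say that the team must alert professionals at once if a participant indicates an intention to harm.

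**The concern.** By the time the 911 sentence applies, a staff member in the home has already concluded that life is at risk. The sentence then adds a further test, whether the services can be reached. Being able to phone is not the same as phoning. Section 1.1 of the protocol describes a strong link between TBI and suicide risk and names initiation and planning among the typical deficits, so leaving the call to the veteran suits this population poorly.

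The situation can arise. Section 4.1.1 lets the veteran choose home for the baseline interview, and item 9 is asked at that visit after consent, so a positive answer can first appear there. Section 10.1 foresees suicidal ideation emerging during the study. At stake is participant safety in a rare but possibly fatal event. Nothing in the sample size or analysis is involved.

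**Working it through.** No arithmetic applies beyond a count. The check is whether any other rule supplies what the home paragraph lacks.

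**Step 1. The rules side by side.**

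| Situation | Who calls | Added condition | Told to stay |
|---|---|---|---|
| Medical emergency, on the phone (alert table) | Staff, 911 | None | Not applicable |
| Medical emergency, home (alert table) | Staff, 911 | None | Yes |
| Immediate threat or positive item 9, clinic (Safety Plan) | Staff, in-house emergency behavioral health | None | Yes |
| Life-threatening emergency, home (Safety Plan) | Staff, 911 | Inability to contact services | No |

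Three of these rows have staff call 911. One of the three carries a condition beyond the emergency itself. The clinic rule relies on in-house services and does not mention 911, so it is comparable only in that staff stay and make the call themselves.

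**Step 2. Who makes the calls in the home paragraph.** It mentions 911 three times. Two are calls the veteran may make (for suicidal ideation and for homicidal thinking) and one is the staff call: 2 + 1 = 3.

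**Step 3. Whose inability.** The natural reading is that the veteran cannot reach services. The grammar could also mean the staff member. The call is conditional either way.

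**Step 4. Which veterans fall outside the rule.**

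- Incapacitated: the condition is met at once and staff call.
- Able and willing to phone: the listed routes (crisis line, on-call psychiatrist, 911, emergency room) serve this veteran.
- Able to phone but does not or will not, and in imminent danger: on a plain reading the condition is not met and the staff 911 call is not triggered.

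Only the third group is affected.

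**Step 5. Whether another rule covers that group.** The medical row is unconditional, so medical emergencies at home are already handled. The psychiatric row defers to the Safety Plan. The clinic rule is limited to the clinic. The training and consent text includes neither a 911 call nor an instruction to stay. The home paragraph is therefore the operative rule.

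**The case against.** The case on the other side is substantial, and most of it limits the size of the point.

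- **Other safeguards exist.** The duty to notify professionals on an indicated intention to harm is immediate, falls on the team, and does not depend on whether the veteran can phone. The opening of the Safety Plan gives the team access to a licensed clinician in and out of business hours. Training covers imminent risk, and Columbia triage mentions safety precautions. A reader might infer that staff at home have nothing beyond referral and encouragement; these provisions show otherwise.
- **Exposure is limited.** Section 4.1.2 makes a veteran with a positive item 9 at baseline ineligible, and Section 7.1 excludes psychosis, a history of bipolar disorder and a history of severe aggressiveness. Home contact occurs only if the participant prefers it. These reduce exposure but do not remove it, because ideation can first surface at a home baseline interview or emerge later.
- **The condition can be read generously.** Staff might treat an acutely suicidal veteran who refuses to call as unable to do so. The text does not define the term, and an emergency instruction should not depend on that interpretation.
- **Sensible staff would call and stay anyway.** Probably so. The written rule should then say it.

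Two stronger readings are not supported. A reader might infer that an overdose at home falls into the gap, but that requires treating the four signs in the medical-emergency row as a closed list, which the table does not say. A reader might also infer that staff must wait before calling or are meant to leave. No waiting step is prescribed, and the paragraph is silent on staying; it does not tell staff to go.

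**Conclusion.** The point stands in its narrow form. For a psychiatric emergency at home that staff have judged life-threatening, the staff 911 call is still conditional and no stay instruction is given. The veteran affected is one in imminent danger who could call but does not or will not. The safeguards above soften the gap without closing it.

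Its size cannot be computed. The documents give neither the share of contacts held at home nor an event rate, and the protocol expects adverse events to be infrequent, so few cases should arise. The conclusion assumes that inability is read plainly and that the training follows the Safety Plan as written. The count of one conditional rule in three describes the wording and does not estimate harm. Design, sample size and analysis are unaffected. This is a cheap improvement that should be made; it does not show that the safety plan as a whole is unsound.

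**What to change.** In the home paragraph of the Safety Plan, delete the clause about being unable to contact services and replace the rule with wording such as: *If the OT or interviewer judges that an emergency in the home is life-threatening, whether medical or psychiatric, that staff member phones 911 at once and remains with the veteran until responders arrive, unless remaining would endanger the staff member.*

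The exception is needed because the same paragraph covers danger to others: "If veterans are experiencing homicidal thinking, they can call 911 or go to VA's emergency room or the nearest emergency room". Keep the present encouragement to seek care for situations that are not life-threatening, and bring the training text into line.

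The cost is one sentence and the matching training material. The downside is an occasional 911 call that the veteran could have made or did not want. There is no cost to design, sample size or analysis.
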